[name]

Ospemifene versus Conjugated Estrogens in the Treatment of Postmenopausal Sexual Dysfunction

[name]

Female Pelvic Medicine and Reconstructive Surgery, Fellow
Emory University

[name], PhD

Female Pelvic Medicine and Reconstructive Surgery, Division Director & Fellowship Director
Associate Professor
Emory University Hospital, Chief of Service

[name], MPH, NCMP

Department of Obstetrics & Gynecology, Associate Professor
Menopause Clinic, Director
Emory University

Abstract & Relevance

57% of postmenopausal women suffer from female sexual dysfunction (FSD). Vulvovaginal atrophy (VVA) is a condition that impacts up to 60% of the growing postmenopausal female population, and the most common symptom is dyspareunia. Women with FSD are 3.84 times as likely to also have VVA. Vaginal estrogen is the most common treatment for VVA, but it only marginally improves overall sexual function, and many women and clinicians avoid using it because of the risks of exogenous estrogen use during menopause. Ospemifene is a SERM that is FDA-approved for dyspareunia related to VVA, and has shown superb improvements in overall sexual health. This oral medication, taken daily, improves vaginal health, and has demonstrated protective activity in the breast and bone tissues. It also has not demonstrated any carcinogenic activity in the endometrium or liver. This study hopes to determine if ospemifene is superior to conjugated estrogens in improving sexual function and vaginal atrophy symptoms. 104 women will be randomized to receive 12 weeks of 60mg oral ospemifene, taken daily, or 12 weeks of 0.5mg vaginal conjugated estrogens, which is placed vaginally twice per week. The improvements in sexual health and VVA symptom severity will be compared in each group. This study will help determine if ospemifene is a better treatment medication than conjugated estrogens. The implications of this study may provide an attractive alternative to the many women who continue to suffer from sexual dysfunction and VVA because of concerns surrounding the use of exogenous hormones.

Introduction

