In 2013, Ospemifene was approved by the Food and Drug Administration for the treatment of moderate to severe dyspareunia that is due to menopause [10]. Ospemifene is a non-estrogen selective estrogen receptor modulator (SERM). SERMs are estrogen receptor (ER) agonist/antagonists that typically induce the desirable effects of estrogen while avoiding estrogen-related adverse effects. Unlike other drugs in this class, Ospemifene has been shown to have significant estrogenic agonist effects on the vagina and bone, but antagonist effects on breast tissue [6]. Furthermore, it significantly improves overall sexual function [12]. Despite this promising medical profile, it remains a second or third line of therapy to treat VVA. More research is needed to determine if ospemifene is an acceptable, and possibly a favorable, alternative to vaginal estrogen for the treatment of vulvovaginal atrophy, especially if there is any concern for sexual function. In this research study, we aspire to determine the efficacy of ospemifene compared to a vaginal estrogen. The primary aim of this research is to compare female sexual function as measured by a validated instrument in women randomized to receive ospemifene and vaginal estrogen. Secondary aims include comparing markers of vaginal health and safety in both treatment groups.

Hypothesis

Ospemifene is a nonhormonal alternative that has proven to significantly improve sexual health and vulvovaginal atrophy, yet vaginal estrogen is still considered the first-line therapy. Our null hypothesis is that ospemifene has a similar efficacy as vaginal conjugated estrogens for improving sexual function in postmenopausal women who have vulvovaginal atrophy.

Specific Aims

Specific Aim 1: *To compare the efficacy of ospemifene and vaginal conjugated estrogens on female sexual function.* Ospemifene is the only non-estrogen that is FDA-approved to treat dyspareunia in postmenopausal women. Further, studies report a significant improvement in sexual health in patients that are treated with ospemifene [12]. However, vaginal estrogen therapy (with conjugated equine estrogen or estradiol) remains the most commonly prescribed treatment for dyspareunia. To our knowledge, a direct comparison of ospemifene and local vaginal estrogen therapy on postmenopausal female sexual function has not been performed. We hypothesize that ospemifene provides a greater improvement in sexual function in postmenopausal women with dyspareunia and VVA.

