To our knowledge, there has been no prior study that reported the prevalence of female sexual dysfunction amongst women using vaginal conjugated estrogens, defined as having an FSFI score of 26.55 or less. With an FSD prevalence of 57%, we determine a 50% reduction in the prevalence to be clinically significant. Setting an alpha of 0.05, and a power of 0.80, and assuming a minimum of 15% dropout rate, the sample size is set to 52 in each group.

Specific Aims

Specific Aim 1: To compare the efficacy of each drug in improving sexual function.

- a. Experimental Design: In this study, participants will be asked to complete the 19-question female sexual function index (FSFI) questionnaire at the beginning of the study period and at 12 weeks. The results will be used to compare the effect of each medication on the various domains of sexual function.

The mean total score in each treatment group at baseline will be compared using Student's t-test. Additionally, the score of the components of desire, arousal, lubrication, orgasm, satisfaction and pain will be similarly compared. Later, the change in these scores between the two treatment groups at 12 weeks will be compared using a paired t-test analysis.

Anticipated Results and Interpretation: We expect to see similar results in this study, showing comparable improvements in vaginal lubrication and dyspareunia, while showing greater improvement for overall sexual health in the ospemifene group.

Potential Pitfalls, Alternative Approaches, and Future Directions: We do not anticipate any challenges with the administration and analysis of this questionnaire.

Specific Aim 2: To compare each drug's impact on VVA symptoms

- a. Experimental Design: Participants will complete a Likert scale of symptom severity at the beginning and at the end of the study. The symptoms listed will include dyspareunia, vaginal dryness, vaginal pain, and vaginal itching. The survey will ask them to rate the severity of each VVA symptom on a scale of 0 to 3, with 0 being none, 1 being mild, 2 being moderate, and 3 being severe. It will also ask them to choose their most bothersome symptom (MBS).

The mean score of the MBS in each treatment group at baseline will be compared using Student's t-test. Later, the change in score of the MBS between the two treatment groups at four weeks and again at 12 weeks will be compared using a paired t-test analysis.

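### Aim 1 compares the FSFI total and six domain scores between arms with no score named as primary and no control of multiplicity, so the chance of a false difference exceeds 5%

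*Combined protocol and SAP*

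**What the plan says.** The Introduction gives the primary aim as to "compare female sexual function as measured by a validated instrument". That names an instrument, not a score.

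In the Specific Aims section that follows Sample Size Analysis, the Experimental Design of Specific Aim 1 says of the FSFI: "The results will be used to compare the effect of each medication on the various domains of sexual function". The baseline mean total is to be compared between arms by Student's t-test, and then: "Additionally, the score of the components of desire, arousal, lubrication, orgasm, satisfaction and pain will be similarly compared". The sentence after that carries the efficacy analysis. It compares the 12-week change in these same scores, total and domains alike, between the two treatment groups, and it names a paired t-test.

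The only significance level is in Sample Size Analysis: "Setting an alpha of 0.05, and a power of 0.80". That calculation concerns the prevalence of female sexual dysfunction, defined as an FSFI score of 26.55 or less: "With an FSD prevalence of 57%, we determine a 50% reduction in the prevalence to be clinically significant". No section designates one FSFI score as primary, orders the seven tests, labels the domains secondary or exploratory, or adjusts for multiplicity.

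**The concern.** The Abstract states the trial's purpose: "This study hopes to determine if ospemifene is superior to conjugated estrogens in improving sexual function and vaginal atrophy symptoms". With seven scores compared under the primary aim and none ranked, the plan does not say what result would establish superiority in sexual function. The difficult case is a trial in which one domain reaches significance and the total does not. The plan neither allows nor forbids reporting that as success.

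The consequences are practical. The Innovation section wants the results to inform whether ospemifene should become first-line treatment. The Overview says that participants and clinicians cannot be blinded, and the FSFI is self-reported. A score that can be singled out after the data are seen weakens the conclusion in a trial of this kind.

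**Working it through.** **Inputs from the documents**
- Alpha 0.05 and power 0.80; prevalence 57%, halved to 28.5%; 15% dropout; 52 per group (Sample Size Analysis).
- Seven scores: FSFI total plus desire, arousal, lubrication, orgasm, satisfaction and pain (Specific Aim 1).

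**Assumptions, not in the documents**
- Each score is tested two-sided at 0.05.
- The test is an independent-samples comparison, since a paired test cannot compare two separate groups.
- The six domains have equal pairwise correlation ρ, shown from 0 to 0.8.
- The total behaves as the equally weighted sum of the domains.

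**1. The plan's own figure.** Two proportions, unpooled variance, two-sided:

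n = (z₀.₉₇₅ + z₀.₈₀)² × [p₁(1−p₁) + p₂(1−p₂)] / (p₁−p₂)²

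= (1.960 + 0.842)² × (0.57×0.43 + 0.285×0.715) / 0.285²

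= 7.849 × 0.4489 / 0.0812 = 43.4, rounded up to 44.

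With dropout, 44 / 0.85 = 51.8, rounded up to 52. The stated figure is reproduced. The plan does not name its formula; the pooled two-sided version gives 47, and 56 after dropout. On either formula the calculation is for a prevalence, not for a mean FSFI score.

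**2. Number of tests.** One total and six domains give seven between-arm tests of change at 12 weeks. The baseline comparisons are left out because they support no efficacy claim. Aim 2 is left out because the Introduction places outcomes beyond sexual function under secondary aims.

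**3. Reference point.** Seven fully independent tests would give 1 − 0.95⁷ = 30.2%. The total is built from the domains, so the true figure is lower.

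**4. Correlated tests.** One million simulated sets of six equicorrelated normal statistics plus their standardised sum, with no treatment difference:

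| Assumed ρ | At least one false difference, either direction | At least one false result favouring ospemifene |
|---|---|---|
| 0 | 28.1% | 14.9% |
| 0.3 | 24.5% | 12% |
| 0.5 | 20.9% | 10.4% |
| 0.7 | 16.4% | 8.2% |
| 0.8 | 13.8% | 6.9% |
| Single test, for comparison | 5% | 2.5% |

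Simulated two-sample t-tests agree: 28.5% (ρ = 0) and 20.5% (ρ = 0.5) at 44 per arm, and 28.3% and 20.8% at 52 per arm.

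**5. Where the excess lies.** The total alone accounts for 5%. The remainder is the chance that some domain is significant while the total is not: 28.1 − 5 = 23.1% at ρ = 0, 20.9 − 5 = 15.9% at ρ = 0.5, and 13.8 − 5 = 8.8% at ρ = 0.8.

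**6. Effect of control.** One designated score gives 5%. Bonferroni over seven (0.05/7 = 0.0071) gives 4.7% at ρ = 0 and 3.6% at ρ = 0.5. Gating works as follows. If the total has no true difference, a domain can be claimed only after a false result on the total, which has probability 5%. If the total does differ, Holm holds the six domains at 5%.

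**7. Power for the mean total.** With 52 × 0.85 ≈ 44 evaluable per arm, the standardised difference detectable with 80% power is (1.960 + 0.842) × √(2/44) = 2.802 × 0.213 ≈ 0.60. The plan gives no FSFI standard deviation, so this cannot be converted to FSFI points.

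**The case against.** The best defence is that the plan points to overall function even though it does not say so formally. The total is named first and the components come in as an addition. The anticipated results expect similar gains in lubrication and dyspareunia and place the ospemifene advantage on overall sexual health. The sample size uses a cut-off on the FSFI score, not on a domain. These are fair signs of where the main interest lies. They still set no decision rule: overall sexual health is not defined as the FSFI total, it appears as an expectation rather than a criterion, and the quantity used for sizing is not among the Aim 1 tests.

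Several limits on the concern do stand. The 0.05 is stated for the sample size; applying it to each FSFI test is an inference, and sidedness is not stated. The error rates assume a between-arm test in place of the paired test that the plan names.

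A reader might go further and infer that the trial has more than a 20% chance of wrongly declaring ospemifene better. The documents do not support that. Figures above 20% count differences in either direction and need correlations of about 0.5 or less. Zero correlation is an extreme assumption for subscales of one questionnaire answered by the same woman. In ospemifene's favour the figure is at most about 15% over the range shown. Nor does any section say that a single significant domain counts as success. The plan leaves that open.

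**Conclusion.** The concern holds in this form: Aim 1 has seven between-arm efficacy comparisons, no designated primary score, no ordering and no multiplicity control. At two-sided 0.05 for each, the chance of at least one false difference is about 14% to 28%, and of at least one favouring ospemifene about 7% to 15%, where a single test would give 5% and 2.5%. Both ranges rest on assumed domain correlations of 0.8 down to 0 and on the other assumptions listed in the working. The size is therefore uncertain, but every value in the range is well above the single-test level. This should be settled before analysis.

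**What to change.** State in Specific Aim 1 that the between-arm difference in FSFI total at 12 weeks is the only confirmatory test, at two-sided 0.05, and that the superiority conclusion on sexual function rests on it alone. Report the six domains with 95% confidence intervals as secondary or exploratory. Make a confirmatory domain claim only if the total is significant, and then with Holm across the six. Holm without that gate would control error over the domains but not over all seven tests.

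Add to Sample Size Analysis that 52 per group was derived for the prevalence of an FSFI score of 26.55 or less, so the stated 80% power does not apply to the mean total. With about 44 evaluable per arm, 80% power corresponds to a standardised difference of about 0.60.

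The cost is a few sentences and no extra participants. The downside is that domain p-values become less favourable, and a domain finding without a significant total could not be presented as confirmatory.

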In May 2013, the Board of Directors of the International Society for the Study of Women's Sexual Health (ISSWSH) and the Board of Trustees of The North American Menopause Society (NAMS) endorsed the term genitourinary syndrome of menopause (GSM). This term encompasses the numerous changes that occur as a result of the decrease in estrogen and other sex steroids, including vaginal atrophy and sexual dysfunction [1]. In a cross-sectional study of US postmenopausal women, those with sexual dysfunction were 4 times more likely to have vulvovaginal atrophy [2]. With the rising elderly population, the impact of VVA and sexual dysfunction on quality of life and health care costs is a growing issue. In 2000, there were 26.25 million women over the age of 60 years old, and this number is expected to almost double by the year 2030 [3]. Currently VVA affects up to 60% of postmenopausal women, and its most common

Updated 11/27/17

Pg. 1

symptom is dyspareunia [4,5]. Further, if left untreated, it can increase rates of infection, and negatively impact a woman's sexual health and quality of life [6]. While only 25% of women with VVA seek medical advice, only 3% of women reveal problems with sexual health without being prompted [7,8].

There are several established methods of treatment for VVA. Vaginal estrogen is considered the treatment of choice. While several studies have shown that vaginal estrogen does not increase serum estrogen levels above postmenopausal values, there is still significant controversy surrounding the use of estrogen and the risk of breast cancer and uterine cancer [9,10]. This study is important because we hope to prove a non-estrogen medication to be an effective non-hormonal alternative therapy for vulvovaginal atrophy.

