Specific Aim 2: *To compare the effects of ospemifene and vaginal conjugated estrogens on symptoms of VVA.* We hypothesize that treatment with either ospemifene or vaginal conjugated

estrogens will demonstrate comparable improvements in VVA symptoms. In the population randomly treated with vaginal conjugated estrogens or ospemifene in specific aim 1, we will compare the change from baseline and between groups.

Significance

Female Sexual Dysfunction

Traditionally, female sexual dysfunction (FSD) is defined as the disorder of desire, arousal, pain and/or muted orgasm in women [28]. While many people may consider this disorder to be pertinent only during reproductive years, it is very common in the menopausal women population, affecting 57% of women in menopause [5]. In 2014, Nappi et al published a review of data that shows the importance of discussing sexual function and vaginal atrophy with postmenopausal women. 1 in 5 women over the age of 70 still engage in intercourse. Moreover, 71% of women agree that, "it was important to them to maintain an active sex life." The article also adds that only 3% of women will seek advice about sexual function if not prompted. Many who do bring this problem to their provider's attention feel as though it is dismissed. Meanwhile, providers tended not to proactively address sexual health for middle and later life-aged women, because of time constraints, inadequate training, personal attitudes and beliefs that sex is not a priority for older patients [29].

What is Vulvovaginal Atrophy?

There is significant overlap between FSD and VVA. Women with FSD are almost 4 times as likely to have VVA [29]. Once a woman reaches menopause, her ovarian production of estrogen decreases dramatically. The vagina and vulva are two organs that are affected by the lack of estradiol in the body. Without estrogen, the vagina epithelial cells decline in maturation, and there is also an increase in the vaginal pH. These changes lead to the common symptoms of painful intercourse, vaginal dryness, pain, and itching. They also put the vaginal epithelium at risk for infection and inflammation. Further, the increase in pH is associated with an increased rate of recurrent urinary tract infections in postmenopausal women [13]. In the US, approximately 60% of women report symptoms related to vulvovaginal atrophy [4].

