Once a qualifying subject is identified, she will be randomized into a treatment group. The participant will be randomized to receive either a vaginal conjugated estrogens prescription or an ospemifene prescription. A computerized randomization program will be used to perform block randomization in random blocks of 4 and 10. Allocations envelopes containing the assignment will be used for the study. They will be sealed opaque envelopes with aluminum foil inside. They will also contain carbon-copy paper. The treatment number will be printed on the envelope. Once the participant has signed the informed consent form, her name will be printed on the envelope, which will transfer over to the carbon-copy paper, and the envelope will be opened.

Study Plan

The patient will be informed of her assigned medication, and she will receive a medication coupon to help offset the cost of the medication. Each medication is FDA-approved for long-term use of at least 52 weeks. For this study, a 12-week prescription for the medication will be sent electron-

[figure not shown]
ically to the pharmacy of her choice. Treatment with estrogen will consist of 0.5 gram of conjugated estrogens placed vaginally for 12 weeks. Treatment with ospemifene will consist of a 60mg tablet that will be taken at the same time daily for 12 weeks.

The patient will receive an intake packet that includes the following information:

1. Copy of signed informed consent form
2. Important contacts and instructions for emergency/adverse events
3. Allocation card
4. Medication's FDA packet insert
5. Instructions on dosing
6. 12-week date to repeat questionnaires

She will be called the following day to confirm her start date of the medication. They will return at 12 weeks and complete the same FSFI and Likert Scale questionnaires regarding sexual function and VVA symptoms. The questionnaires may also be completed over the phone with the investigator.

Alternatively, if time during clinic is limited, the patient can be consented and allocated to a medication in person, by a co-investigator. She will be called by a co-investigator on the same day to complete the enrollment and questionnaires. Below is a summary of the study plan.

Sample Size Analysis

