Anticipated Results and Interpretation: Similar to objective findings, prior studies have shown significant improvement in VVA symptoms in patients using ospemifene or vaginal estrogen. We anticipate that the improvements seen with ospemifene will be comparable to those seen with vaginal estrogen.

Potential Pitfalls, Alternative Approaches, and Future Directions: The Likert scale is commonly used to assess symptom improvement in VVA treatment studies. We do not anticipate any pitfalls in this specific aim.

Safety Monitoring

Participants in the study will be provided with contact information to be used in the case of an adverse event related to the medication. For emergencies, they will be instructed to dial 911 and/or seek immediate medical attention. They will be instructed to contact the study team at [contact], to inform the team about any adverse event that may be related to the medication.

All reports of injury will be logged in one password-protected electronic file, by members of the study team. Patient data, including adverse events will be reviewed every two weeks by the [name] and [name]. Appendix 1 shows adverse events that have been documented during prior clinical trials of the two medications. This data will be used to determine whether the study will be discontinued due to occurrence or frequency of any given adverse event.

Individual Stopping Rules

Any event that involves new onset of vaginal bleeding, cardiovascular event, venous thromboembolism, or new diagnosis of cancer, will require the individual to discontinue the medication and withdraw from the study.

Timeline

Item	Start	Complete/Submit
IRB application	Started	November 1, 2016
Grant/Funding applications	Started	February 2017
Subject recruitment	November 1, 2016	August 1, 2017
Data Analysis	March 1, 2017	August 30, 2017
Thesis/Report	November 15, 2017	December 1, 2017

Required Resources & Budget

Resource	Estimated Cost
Personnel	
Consent forms, severity scale, questionnaire, other paper documents	
Counseling office	

\$10 gift cards for return visit, 104 subjects	\$1040.00
--	-----------

References

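### The between-arm test of 12-week change is named as a paired t-test, but the arms are independent groups with no pairs

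*Combined protocol and SAP*

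**What the plan says.** The design is two parallel arms. Under Randomization and Allocation Concealment: "The participant will be randomized to receive either a vaginal conjugated estrogens prescription or an ospemifene prescription". Allocation is in blocks of randomly varying size (4 or 10), and no matching, crossover or pairing of women is described.

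The tests are named in the Specific Aims section that follows the Sample Size Analysis:

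- **FSFI, baseline:** Student's t-test between arms, for the total score and, in the same way, the six domains.
- **FSFI, 12 weeks (Specific Aim 1):** "Later, the change in these scores between the two treatment groups at 12 weeks will be compared using a paired t-test analysis".
- **MBS, baseline:** Student's t-test between arms.
- **MBS, follow-up (Specific Aim 2):** "Later, the change in score of the MBS between the two treatment groups at four weeks and again at 12 weeks will be compared", again with a paired t-test.

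The earlier Specific Aims section, under Aim 2, says "we will compare the change from baseline and between groups" but names no test. No two-sample test of change, ANCOVA, rank test or test of proportions is named anywhere for a 12-week outcome.

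**The concern.** A paired t-test analyses differences within defined pairs. Across these two arms there are none. The FSFI sentence can be read in three ways:

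1. **Literal.** Women in opposite arms are paired by some arbitrary order. The p-value then depends on that order, and completers without a partner are dropped whenever the arms finish with different numbers.
2. **Within-arm.** Baseline is tested against 12 weeks separately in each arm. That is a valid paired test, but it does not compare the drugs.
3. **Naming slip.** Each woman's change is calculated and the changes are compared between arms with a two-sample test.

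Only the third answers the primary aim given in the Introduction, a comparison of sexual function between the randomised groups, and the text does not specify it. The trial is open-label, so a choice left to the analyst could be made with allocation known.

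**Working it through.** **Inputs from the plan.** 52 per arm; dropout of at least 15%; alpha 0.05; power 0.80; FSD prevalence 57% with a 50% reduction, so 0.57 against 0.285. The plan gives no SD for change in FSFI or MBS, so effects below are in assumed SD units. Sidedness is not stated; two-sided is assumed.

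**1. The plan's own sample size.** With the unpooled formula for two independent proportions:

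n = (1.96 + 0.8416)² × [0.57×0.43 + 0.285×0.715] / (0.57 − 0.285)² = 7.849 × 0.4489 / 0.0812 = 43.4, so 44 per arm.

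44 / 0.85 = 51.8, so 52 per arm, which matches "assuming a minimum of 15% dropout rate, the sample size is set to 52 in each group". The plan does not name its formula, but this one reproduces the figure and treats the arms as independent groups. Correcting the t-test therefore does not alter N.

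**2. Could completers be paired off?** With 52 per arm and independent dropout d, the chance of equal completer numbers is the sum over k of Binom(k; 52, 1−d)².

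| Dropout d | Equal completer numbers | Mean number without a partner |
|---|---|---|
| 15% | 11.0% | 2.9 |
| 20% | 9.8% | 3.2 |
| 25% | 9.0% | 3.5 |

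**3. Average effect of random pairing.** With 44 per arm the degrees of freedom fall from 86 to 43, and the critical t rises from 1.988 to 2.017. In 100,000 simulated normal trials:

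| | Paired on arbitrary pairs | Two-sample | Verdicts differ |
|---|---|---|---|
| No true difference (type I error) | 5.1% | 5.1% | 1.4% |
| Assumed difference 0.6 SD (power) | 78.4% | 79.4% | 3.6% |

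**4. Dependence on the pairing.** 300 simulated data sets were shifted so that the two-sample p was 0.049, and each was re-paired 1,000 times. The paired p ran on average from 0.026 (5th percentile) to 0.081 (95th percentile), and 45% of orderings gave p < 0.05.

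**5. The within-arm reading.** If the drugs have equal true effects and each arm's paired test has power p, exactly one arm is significant with probability 2p(1−p). At n = 44 (noncentral t):

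| Assumed standardised within-woman change | p | 2p(1−p) |
|---|---|---|
| 0.3 | 0.494 | 50% |
| 0.4 | 0.737 | 39% |
| 0.5 | 0.900 | 18% |
| 0.6 | 0.973 | 5.2% |
| 0.7 | 0.995 | 1.0% |

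Without an SD, the trial's place in this range is unknown.

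**6. What the corrected test can detect.** A two-sample t-test at two-sided 0.05 and 80% power detects a difference in mean change of 0.60 SD with 44 per arm, or 0.55 SD with 52 per arm.

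**The case against.** The strongest reply is that this is a wrong label. The sentence already states the quantity of interest, the between-group difference in change. Student's t-test is correctly used between arms at baseline, the sample size reproduces with independent groups, and *paired* may loosely refer to each woman's before-and-after scores. A competent statistician would run a two-sample test. I agree that this is the likeliest intent. But the plan names two different tests and assigns the paired one to the between-arm comparison, twice, so the reader has to override the text to obtain a usable primary analysis. The protocol's statement on change from baseline and between groups gives limited help: it sits under the VVA-symptom aim and also fits a within-arm test plus a between-arm one.

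Several points on size stand:

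- Nothing suggests that the investigators meant to pair women across arms, and the average harm if they did is small.
- The 45% figure describes data sets placed at the decision boundary, where any perturbation changes many verdicts.
- The within-arm figures mislead only if significance in one arm alone were read as a drug difference, a rule the plan does not state.

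It is also fair that the trial is sized on a binary outcome, FSFI at or below 26.55, for which no test is named. Correcting the t-test does not close that gap.

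**Conclusion.** The concern holds and must be fixed. The only test named for the 12-week comparison of the drugs does not fit a parallel-group design and cannot be run as written without inventing pairs. The rating rests on that specification error, not on the simulations: under random pairing, type I error is unchanged and power falls by about one percentage point. What is lost is a determined result. The simulated figures assume normal changes with equal SDs, independent dropout and two-sided testing; the conclusion about the wording needs none of these.

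**What to change.** **Required.** In both sentences, replace the paired t-test with an independent two-sample t-test on each woman's change from baseline, reporting the between-group difference in mean change, its 95% confidence interval and the two-sided p-value.

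**Preferred.** Use ANCOVA of the 12-week score on treatment with the corresponding baseline score as covariate, reporting the same quantities. If it is adopted, declare it primary and keep the t-test as supporting, so that the choice is not reopened. With equal SDs at baseline and 12 weeks, the variance ratio to change scores is (1+r)/2, a reduction of 35%, 25% or 15% at an assumed correlation r of 0.3, 0.5 or 0.7. With a 12-week SD 1.25 times baseline the reductions are about 22%, 11% and 2%; at 0.8 times, about 50%, 43% and 37%.

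**MBS.** It is a single 0 to 3 item, so add a rank-sum test of change as a sensitivity check.

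**To be settled separately.** The four-week MBS comparison conflicts with the collection schedule ("Participants will complete a Likert scale of symptom severity at the beginning and at the end of the study"), and the binary FSD outcome needs its own named test. Dropping the baseline t-tests is optional.

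**Cost.** The required change rewords two sentences, with no new data and no change in N. However, the document is marked "Updated 11/27/17" and the Timeline has data analysis finishing on "August 30, 2017". If outcomes have already been analysed, report the correction as a change to the plan and say when it was made.
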